6.4 POST- GENE TRANSFER MONITORING

- Subjects will return to a designated bed following gene transfer with close monitoring of vital signs. CK levels will be checked after the procedure. Concomitant medications and all adverse events/serious adverse events will also be monitored and documented following injection. Subjects will be discharged the day after gene transfer (if no adverse side effects are observed).

Subjects will return for follow up visits on days 2, 7, 14, 30, 60, 90 and 180 and at months 9 (physical therapy and immunology only), 12, 18, and 24. Toxicity monitoring on each of these dates (except visit 9) (including day 1-2 post-gene transfer) will include:

- Physical Exam
- GGT* will be drawn as above and at 45 and 75 days post gene transfer to assess delayed sub-clinical hepatitis. GGT is assessed in preference to ALT/AST which are elevated in muscular dystrophy.
- Total bilirubin

- Glucose
- PT/PTT/INR
- CBC/Diff/Platelet with smear
- Serum Creatine kinase (CK)
- Creatinine/BUN
- Cystatin C
- Alkaline phosphatase
- AST
- Amylase
- ALT
- Electrolytes
- Total Protein
- Urinalysis
- Immune studies (day 7 visit and after)
- [REDACTED]
- [REDACTED]
- [REDACTED]
- [REDACTED]

- Six minute walk test (6MWT). (60 day visit and after)

- [REDACTED]

- [REDACTED]

- Photograph of incision site and surrounding area to be completed until day 14

** Subjects will be required to avoid alcohol the week before testing. For subjects taking drugs that potentially induce GGT synthesis through the cytochrome P450 system, the clinically significant range will be estimated at two times the levels obtained from the baseline screening test.*

Because of the possible concerns with viral shedding, all sexually active participants will be asked to refrain from sexual intercourse or practice barrier contraception for six months (females) or until two consecutive semen samples (adult males) are tested negative for the presence of vector. As part of this study we must ask for a semen sample from all sexually active males 18 years and older.

Semen samples will be requested on day 90 from all sexually active males age 18 years or older, for PCR analysis for vector genomes. This interval is based on selecting a date post-gene transfer that is longer than the 70 days required from the beginning of the first meiotic division to the completion of spermatogenesis. As mature sperm spend an additional 5-15 days in the epididymis, a date three months after gene transfer is therefore optimal to look for any possible germ line incorporation. Testing will continue until 2 consecutive negative samples are obtained.

Blood samples will be obtained for immune studies at days 7, 14, 30, 60, 90, 180 post gene transfer and 9, 12, 18, and 24 months; this will include testing for binding antibody to rAAVrh74, as well as ELISpot to detect T cell response to capsid antigens. GGT will be measured at 45 and 75 days post gene transfer to assess delayed sub-clinical hepatitis.

6.5 LONG-TERM MONITORING

Subjects will be seen at the end of 1st and 2nd years for a physical exam, strength testing, and immune studies. We will follow the most recent FDA guidelines with regard to long-term subject follow up following gene transfer. As discussed and based on prior experience with rAAV or transgene, there is a very low probability of gene transfer-related delayed adverse events. We will, however, evaluate short-term safety over a two-year period that incorporates the active phase of the protocol. If newly identified risks are associated with our product, or if the subjects suffer any adverse events during this period, we will initiate a long-term follow-up according to the FDA guidelines.

6.6 OUTCOME MEASURES

The study is a Phase I/IIa clinical trial inclusive of safety and efficacy outcome measures

- A. Safety is the primary outcome for this clinical gene transfer trial. Stopping criteria are based on development of unacceptable toxicity defined as the occurrence of any one Grade III or higher treatment-related toxicities, or two or more Grade II treatment-related toxicities.

B. Efficacy outcome measures include:

i. Strength and functional testing will be performed at baseline and at days 60, 90, 180, and at 9, 12, 18, and 24 months. This will include the 6MWT distance as the primary functional variable. [REDACTED]

[REDACTED]

[REDACTED]

[REDACTED]

[REDACTED] Pre- and post-treatment strength, distance, and time will be evaluated by using paired t-tests.

[REDACTED]

[REDACTED]

[REDACTED]

[REDACTED]

[REDACTED]

[REDACTED]

[REDACTED]

[REDACTED]

[REDACTED]

[REDACTED]

[REDACTED]

[REDACTED]

iii. Immune response will be assessed by IFN- γ ELISpots to alpha-sarcoglycan and AAV capsid. A rise in IFN- γ of 50 spot forming colonies per one million PBMCs towards virus or transgene will be considered significant. An additional measure of immune response will be the binding antibody assay to AAV.

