7.4 DOSE LIMITING TOXICITY

In reporting adverse events we will follow the final regulations issued by the Food and Drug Administration addressing the safety reporting requirements for investigational new drug applications (INDs) found in 21 CFR part 312 and for bioavailability and bioequivalence studies found in 21 CFR part 320. "Safety Reporting Requirements for INDs and BA/BE Studies".

<http://www.fda.gov/downloads/Drugs/GuidanceComplianceRegulatoryInformation/Guidances/UCM227351.pdf>

The classification for adverse events to be used is the following:

- 1 Mild adverse event; did not require treatment
- 2 Moderate adverse event; resolved with treatment
- 3 Severe adverse event; inability to carry on normal activities; required professional medical attention
- 4 Life-threatening or permanently disabling adverse event
- 5 Fatal adverse event

In this grading system, “**severe**” is not equivalent to *seriousness*.

The definitions to be employed will follow the final regulations issued by the FDA in September 2010 “Safety Reporting Requirements for INDs and BA/BE Studies”, and described in section 7.4 of this protocol.

Dose limiting toxicity (DLT) is defined as any adverse event that is possibly, probably, or definitely related to the study agent. This would include any grade 3 event according to the classification given above.

Study enrollment will be halted by the investigators when any subject experiences a Grade 3, or higher adverse event toxicity that is possibly, probably, or definitely related to the study drug.

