Laboratory tests with values within the clinically significant range will be repeated during the same visit whenever possible (refer to Table 6.4 for a complete list of clinically significant range values). If the test result returns after the subject leaves the clinic, they will be immediately contacted. For local residents they will be asked to return to the outpatient clinic for a repeat test as clinically indicated. For non-local residents, arrangements will be made to have the blood test redrawn in a laboratory close to home or by their primary care physician. To avoid any confusion for the primary care physician, they will be informed (with permission from the subject) of their participation in the study at the time of gene transfer. If the AE requires treatment, this will be carried out by the primary care physician or a doctor of choice selected by the subject. We will obtain copies of repeat laboratory tests and any relevant medical records for addition to the subject’s research chart.

Only those adverse events requiring treatment will qualify as DLT. The PI will fulfill the reporting responsibilities under 21 CFR 312.32(c), to notify FDA in an IND safety report of potentially serious risks, as soon as possible, but no later than 15 calendar days after the investigator receives the safety information and determines that the information qualifies for reporting. The investigator will confer with the DSMB and FDA before continuing enrollment.

Table 6.4 Clinically Significant Laboratory Range

Test	Units	Reference Range		Clinically Significant Range
Hemoglobin	g/dL	2Y – 5Y	11.5 – 13.5	< 8.0 or > 18
		6Y – 11Y	11.5 – 15.5	
		12Y – Adult	12.0 – 16.0	
WBC	K/cu mm	4Y – 5Y	5.5 – 15.5	≤3.5 or ≥ 20
		6Y – 9Y	5.0 – 14.5	
		10Y – 20Y	4.5 – 13.5	
		21Y – Adult	4.5 – 11.0	
BUN	mg/dL	5 - 18		≥35
PT	sec	12.4 – 14.7		≤ 5.0 or ≥ 35.0
PTT	sec	24 - 36		≥ 125
Platelet	K/cu mm	140 - 440		≤ 90 or ≥ 800
Amylase	U/L	0 – 17Y	<110	≥ 200
		18Y – Adult	30 - 110	
Total Protein	g/dL	3Y – 15Y	5.8 – 8.7	≤4.4 or ≥ 9.5
		16Y – Adult	6.4 – 8.4	
Total Bilirubin	mg/dL	0.1 – 1.0 mg/dL		≥ 3.0
Creatinine	mg/dL	4Y – 7Y	0.3 – 0.8	≥ 1.8
		8Y – 10Y	0.3 – 0.9	
		11Y – 12Y	0.4 – 1.0	
		13Y – 17Y	0.5 – 1.2	
		18Y – Adult	0.6 – 1.3	
GGT*	U/L	8 – 78		3XULN

ULN= upper limit normal

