7.5 STOPPING/DISCONTINUATION RULES

An independent Data Safety Monitoring Board (DSMB) will be established by the sponsoring agency including a safety monitor for the study. Safety data will be monitored on a continual basis throughout the trial. The DSMB can recommend early termination of the trial for reasons of safety. Study enrollment will be halted by the investigators when any subject experiences a Grade 3, or higher adverse event toxicity that is possibly, probably, or definitely related to the study drug. This will include:

- Grade 3
 - Severe or medically significant but not immediately life-threatening;
 - Hospitalization or prolongation of hospitalization indicated;
 - Disabling; limiting self care ADL**.
- Grade 4
 - Life-threatening consequences;
 - Urgent intervention indicated.
- Grade 5
 - Death related to AE.

Activities of Daily Living (ADL)

*Instrumental ADL refer to preparing meals, shopping for groceries or clothes, using the telephone, managing money, etc.

****Self care ADL refer to bathing, dressing and undressing, feeding self, using the toilet, taking medications, and not bedridden.**

If after review by the DSMB the decision is made to continue, the study will proceed according to Section 6.2.7.6 (Dose escalation) of this protocol.

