7.6 DOSE ESCALATION

There will be 4 weeks between dosing of subjects within a cohort. For the first cohort, the allowance of four weeks between dosing of subjects provides time for safety review from five time points (days 1, 2, 7, 14 and 30) prior to dosing of the next subject and time for review of the safety analysis of all the subjects within a cohort by the investigators and the DSMB.

This timeline will also provide time for review of any clinically significant improvement based on the 6MWT data. [REDACTED]

[REDACTED]

The investigators will confer with the IRB, DSMB, and FDA/CBER on all grade – 3 or higher adverse events that are possibly, probably, or definitely related to the study agent before continuing enrollment. Based on the outcome of the safety and efficacy analysis at the end of each cohort decisions will be made to proceed with dose escalation for the following cohort.

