- A timeline outlining the study progress relative to visit number for each participant, as well as time points for each SAE/Dose Limiting Toxicity. A total for Adverse Events (AEs) for each participant should be included.
- A summary of AEs by severity levels;
- A listing of AE details grouped by participant;
- A listing of SAE details grouped by participant;
- A listing of deaths
- A summary of clinically significant laboratory test results
- A listing of protocol deviations

Stopping/Discontinuation Rules

An independent Data Safety Monitoring Board (DSMB) has been approved by the study's sponsor (National Institute of Health). Safety data will be monitored on a continual basis throughout the trial. The DSMB can recommend early termination of the trial for reasons of safety. Study enrollment will be halted and discussed with the DSMB by the investigators when any subject experiences a Grade 3 or higher adverse event toxicity that is possibly, probably, or definitely related to the study drug. This will include any subject death, important clinical laboratory finding, or any severe local complication in the injected area related to administration of the study agent. If after review by the DSMB, IRB, IBCSC, NIH-OBA and FDA,

the decision is made to continue, the study will proceed according to Dose Escalation plan.

MEMBERSHIP

The DSMB membership consists of persons completely independent of the investigator who have no financial, scientific, or other conflicts of interest with the trial. Current or past collaborators or associates of [REDACTED] must note any conflict of interest before their eligibility to serve on the DSMB is approved.

The DSMB will include experts in or representatives of the fields of:

- Neurology and Neuromuscular Diseases
- Immunology
- Gene Therapy
- Muscular Dystrophy Clinical Care
- Clinical Research and Clinical Trials

Conflict of Interest

Individuals invited to serve on the DSMB as either voting or non-voting members must disclose any potential conflicts of interest, whether real or perceived. Conflicts of interest can include professional, proprietary, and miscellaneous interests as described in the NIH Grant Policy Statement and 45 CFR Part 94. Potential conflicts that develop during a member's tenure on a DSMB must also be disclosed. Written documentation attesting to an absence of conflict of interest is required annually.

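### Protocol 6.6 stops on two related Grade II toxicities, but 7.4, 7.5 and 12.1 halt automatically only on related Grade 3 or higher; the DLT wording is ambiguous and the SAP does not say which rule governed

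*Protocol*

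**What the plan says.** **Halt rule.** Protocol 6.6 (A) bases stopping on "unacceptable toxicity defined as the occurrence of any one Grade III or higher treatment-related toxicities, or two or more Grade II treatment-related toxicities". Protocol 7.5 says "Study enrollment will be halted by the investigators when any subject experiences a Grade 3, or higher adverse event toxicity", provided the event is at least possibly related to the study drug; 7.4 has the same sentence. The DSMB plan in 12.1 says "Study enrollment will be halted and discussed with the DSMB by the investigators when any subject experiences a Grade 3 or higher adverse event", with the same relatedness condition, and adds that the halt covers deaths, important laboratory findings and severe local complications. Protocol 7.6 requires a conference with the IRB, DSMB and FDA on Grade 3 or higher "adverse events that are possibly, probably, or definitely related to the study agent before continuing enrollment".

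**Grading.** The 7.4 scale defines Grade 2 as "Moderate adverse event; resolved with treatment" and Grade 3 by inability to carry on normal activities and need for professional medical attention. Sections 7.5 and 8.1 and SAP 6.6.2 use different wording, based on the level of intervention and on limits to instrumental or self-care activities.

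**DLT.** Protocol 7.4 says "Dose limiting toxicity (DLT) is defined as any adverse event that is possibly, probably, or definitely related to the study agent", which includes any Grade 3 event. Later in the same section it says "Only those adverse events requiring treatment will qualify as DLT". After a sentence on FDA reporting it adds "The investigator will confer with the DSMB and FDA before continuing enrollment".

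**SAP.** SAP 2.2 repeats the aim of establishing an MTD from toxicity. In the visible text, DLT appears only in the abbreviation list.

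**The concern.** The section on outcome measures and the sections on halting and escalation should give the same answer for the same events, and on their face they do not. Someone applying 6.6 would stop after two related Grade II toxicities. Someone applying 7.5 or 12.1 would have no automatic reason to.

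With seven subjects, one or two events decide the safety conclusion, and the MTD aim rests on what counts as dose-limiting. Enrolment was planned to finish in December 2017 (Protocol 11.6.3) and the SAP is dated April 2022, so the live issue is reporting: which rule governed, and whether it was met.

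**Working it through.** The documents state no halt probability, so there is no figure of theirs to reproduce.

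**1. The same events under each section**

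| Related events | 6.6 | 7.4, 7.5, 12.1 | 7.6 |
|---|---|---|---|
| One Grade 3 or higher | Stop | Halt | Confer |
| Two Grade II, none higher | Stop (counting unit not given) | No automatic halt | No conference required |

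**2. Grading.** Take an event that prevents normal activities and needs outpatient medical attention, but only noninvasive treatment. It is Grade 3 on the 7.4 scale and can be Grade 2 on the 8.1 scale. The halt sentence is the same in 7.4 and 7.5, but the scale beside it differs.

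**3. DLT.** The two sentences in 7.4 allow two readings:
- As separate definitions, a mild untreated related event is a DLT under the first and not under the second.
- As one narrowed definition (related and treated), an untreated related Grade 3 event is not a DLT, although it halts enrolment.

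The choice affects 48-hour reporting (8.3) mainly below Grade 3, because 8.1 treats Grades 3 to 5 as SAEs, which 8.3 also sends within 48 hours.

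**4. SAP tables.** None of the seven summaries in 6.6.2, the four per risk in 6.6.2.1 or the rows of the overview table crosses relatedness with grade. If SAE means Grades 3 to 5, related Grade 3 or higher events largely appear in the treatment-related TESAE table. Related Grade 2 events can be counted only from listings.

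**5. Illustration of size.** Inputs: cohorts of 1, 3 and 3 (Protocol synopsis; SAP 2.3). Assumptions, because the documents give no toxicity rate: each subject independently has at most one related Grade II event, with probability p of 10%, 20% or 30%, and the event is known before the next subject is dosed. Only triggers reached before the last dosing count, since after that there is nothing left to halt.

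*Counted per cohort.* Cohort 1A (n=1) cannot trip. Cohort 1B has three subjects, and the first two of Cohort 2 precede the last dosing. With P3 = P(at least 2 of 3) = 0.028, 0.104, 0.216, the probability is 1 − (1 − P3)(1 − p²):
- p = 10%: 1 − 0.972 × 0.99 = 0.038
- p = 20%: 1 − 0.896 × 0.96 = 0.140
- p = 30%: 1 − 0.784 × 0.91 = 0.287

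*Counted over the trial.* First six subjects, 1 − (1 − p)⁶ − 6p(1 − p)⁵:
- p = 10%: 1 − 0.531 − 0.354 = 0.114
- p = 20%: 1 − 0.262 − 0.393 = 0.345
- p = 30%: 1 − 0.118 − 0.303 = 0.580

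*Counted per subject.* Zero under the one-event assumption.

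These are chances of meeting the Grade II limb, not of an extra halt. If each subject also independently has a 10% chance of a related Grade 3 or higher event, none occurs in the first six with probability 0.9⁶ = 0.531. Multiplying, the Grade II limb alone would halt in about 2%, 7% and 15% (per cohort) or 6%, 18% and 31% (over the trial).

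**The case against.** The strongest reply is that Grade II events are not ignored outside 6.6. Protocol 6.7 shares data with the DSMB subject by subject, and the DSMB may recommend termination on safety grounds. Section 12.1 extends the halt to important laboratory findings. The conference sentence in 7.4 can be read as applying to every DLT, in which case one treated related Grade II event already requires talks with the DSMB and FDA, sooner than 6.6 would act. This stands, and it narrows the gap to an automatic stop in 6.6 against discretion or a conference elsewhere. A reader might infer that Grade II events had no oversight; the documents do not support that.

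The scale is also mostly settled. Section 7.5 uses the 8.1 wording for Grades 3 to 5, and SAP 6.6.2 says the investigator grades on the 8.1 scale, so only 7.4 departs. Nor do the two DLT sentences have to be rival definitions, since they can be read as one narrowed definition. Both replies stand, though that narrowed definition leaves out untreated related Grade 3 events.

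A SAP would not normally set an enrolment halt rule, and with seven subjects the listings allow related events to be counted by grade. That is fair. What listings cannot supply is the rule to count against.

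Protocol 11.3.2.11 reports cases of myoglobinuria from rhabdomyolysis within this study, and it is tempting to infer that the conflict affected them or that a stopping rule was breached. The documents do not support that: they give neither the number of cases nor their grade or relatedness call. SAP 6.6.2.1 already gives rhabdomyolysis its own tables by relatedness and, separately, by severity.

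Finally, parts of 6.7 and 7.6 are redacted and could hold a reconciling sentence. The visible rules would still disagree.

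**Conclusion.** The concern holds as an internal contradiction in a decision threshold for the sole primary outcome. Two related Grade II toxicities meet the 6.6 stopping criterion, with no counting unit stated, but do not automatically halt enrolment under 7.4, 7.5 or 12.1 and do not require the 7.6 conference. The odd scale and ambiguous DLT text in 7.4 add to this, and the visible SAP carries the MTD aim without an operative DLT definition.

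On assumed Grade II rates of 10%, 20% and 30%, the limb would be met before the last dosing in about 4%, 14% and 29% of trials (per cohort) or 11%, 34% and 58% (over the trial). The figures depend on the assumed rates, independence, one event per subject and prompt onset; later onset lowers them. They show that the choice of rule and counting unit can matter, not that it changed anything here. The point is worth fixing because the fix is cheap.

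**What to change.** **In the SAP (6.6.2) or the report:**
1. State which halt rule and which DLT definition governed, and confirm that events were graded on the 8.1 scale.
2. Flag subjects meeting the rule and give counts by cohort.
3. Add one table of treatment-related TEAEs by maximum grade.

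**If the protocol is amended or reused:**
1. Delete the 7.4 scale and use the 8.1 scale throughout.
2. State one halt rule identically in 6.6, 7.4, 7.5 and 12.1, and align 7.6. The default is any related Grade 3 or higher event, plus the Grade II limb with a stated counting unit unless the DSMB removes that limb.
3. State one DLT definition that includes every related Grade 3 or higher event, treated or not.

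**Cost:** a paragraph, a derived flag and a table, plus protocol wording if amended. No new data are needed if the 8.1 scale was used; if the 7.4 scale was used, related events in seven subjects need regrading.

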6.7 STATISTICAL ANALYSIS

- [REDACTED]
- [REDACTED]
- [REDACTED]
- [REDACTED]
- [REDACTED]

Data will be shared with the DSMB as gathered for each study subject. Related serious adverse events will be discussed with the DSMB and reported to the FDA.

Note: There will be a flexibility of +/- 7 or +/- 21 working days as outlined for each of the planned study visits including screening to adjust the schedule to any unanticipated event. There will also be potential additions to care based on best medical management if the need arises including additional fluids to restore blood volume.

7.0 TEST MATERIAL AND ADMINISTRATION

[figure not shown]
7.1 DESCRIPTION OF BIOLOGICAL PRODUCT

The biological product is a non-replicating self complementary recombinant adeno-associated virus termed scAAVrh74.tMCK.hSGCA. The vector contains the human alpha-sarcoglycan gene under the control of a triple E-box muscle creatine kinase (tMCK) muscle specific promoter. This cGMP product was produced at the Clinical Manufacturing Facility (CMF) at Nationwide Children's Hospital using practices consistent with the US Food and Drug Administration's "Guidance for Industry – cGMP for Phase 1 Investigational Drugs", July 2008. The material produced will be used to support a vascular delivery phase I/IIa clinical trial. The manufacturing process includes procedures and practices to ensure the safety, identity, quality, purity and strength of the manufactured biologic. The HEK293 cell bank used in the production of the product meets specifications for product release as detailed in FDA and ICH guidelines. The production process is governed by over 100 standard operating procedures (SOP) and production documents. [REDACTED]

[REDACTED] The vector is supplied as a frozen liquid that is thawed before dilution and clinical administration. The vector DNA structure is illustrated below.

Self-Complementary scAAVrh.74.tMCK.hSGCA

